## 12 EVALUATION OF SAFETY PARAMETERS

The analysis of safety will be based on the safety population.

All AEs (including events likely to be related to the underlying disease, or a concomitant illness or medication or clinically significant abnormalities in laboratory parameters or vital signs) will be displayed in summary tables and listings.

Incidences of adverse events will be given as numbers and percentages of subjects with:

- Any AE.
- Any SAE.
- Any AE probably or possibly related to the IMP.
- Any AE temporally related (within 24 hours after end of infusion) to the IMP.
- Any severe AE.
- Any withdrawal due to AE.
- Any AE by Medical Dictionary for Regulatory Activities (MedDRA) preferred term (descending frequency).
- Any AE temporally related (within 24 hours after end of infusion) by MedDRA preferred term (descending frequency).
- Any AE by MedDRA system organ class (SOC).
- Any AE temporally related (within 24 hours after end of infusion) by MedDRA SOC.

Summary tables for AEs will be given by SOC and preferred term. Additionally, AEs will be summarised by severity and relationship to the IMP.

The MedDRA coded terms and the corresponding original (verbatim) terms used by the investigator will be listed.

For laboratory variables (analyses of haematology, clinical chemistry, and thrombogenicity), the mean, standard deviation, median, and range will be presented per time point. Laboratory variables will also be presented graphically. Intra-individual changes between pre-infusion and the respective post-infusion time points will be analysed using shift tables and graphical presentations. Fibrinogen inhibitor testing data will be summarized in frequency tables.

For vital signs, the mean, standard deviation, median, and range will be presented per time point (original values and intra-individual changes between pre-infusion and the respective post-infusion time points). Physical examination data will be presented in frequency tables.

All adverse events for each subject will be listed in Appendix 16 of the CSR, featuring the following data:

- Subject identifier and characteristics (age, sex, weight)
- The adverse event (preferred term, reported term)
- Onset, date of resolution and duration of the adverse event
- Severity (mild, moderate, severe)
- Seriousness (serious/non-serious)
- Action taken - General (none, drug therapy, tests performed) and on study drug (dose not changed, product withdrawn, dose reduced, dose increased)
- Outcome (recovered, recovering, not recovered, recovered with sequelae, fatal, unknown)
- Causality assessment (probable, possible, unlikely, not related)
- Study treatment at time of event or most recent study treatment taken, including dose and batch number
- Previous exposure to fibrinogen treatment (exposure days and total amount used)

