### 2.2 Secondary Objectives

The secondary objectives are:

- To determine the single-dose pharmacokinetics of *Octafibrin* in paediatric subjects with congenital fibrinogen deficiency
- To investigate an association between the overall clinical assessment of haemostatic efficacy and the surrogate endpoint ‘clot strength’ or ‘clot firmness’ (referred to as ‘maximum clot firmness’ [MCF] in this protocol) that was used as a surrogate endpoint for haemostatic efficacy and determined via thromboelastometry (ROTEM) in the pivotal PK study FORMA-01. Therefore, MCF as surrogate efficacy parameter will be determined before and after the first infusion of IMP for treatment of a bleeding episode.
- To achieve a peak target plasma fibrinogen level of 100 mg/dL in minor bleeds and 150 mg/dL for major bleeds 1 hour post-infusion
- To determine the response to *Octafibrin* based on incremental in vivo recovery (IVR)
- To demonstrate the efficacy of *Octafibrin* in preventing bleeding during and after surgery
- To assess the safety of *Octafibrin* in subjects with congenital fibrinogen deficiency, including immunogenicity, thromboembolic complications, and early signs of allergic or hypersensitivity reactions

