### 5.5.2 Method of Administration

*Octafibrin* will be administered as intravenous (i.v.) bolus injection not exceeding an injection rate of 5 mL per minute.

**NOTE:** In this study, **only bolus injections** of *Octafibrin* are permitted. Continuous infusion is not allowed.

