#### *Pre-infusion assessments:*

- TEE questionnaire
- Blood draw for (within 30 minutes before infusion):
  - fibrinogen plasma level (local lab–activity; central lab–antigen and activity)
  - thrombogenicity

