## 7.4 Safety Assessments

Any of the following drug safety information shall be collected:

- All AEs occurring between the start of the first *Octafibrin* infusion and the end of the PK phase, the end of each 30-day observation and follow-up period for on-demand treatment, or the end of the surgical observation period will be recorded.
- All SAEs occurring after the first *Octafibrin* infusion will be documented and reported for a patient throughout the duration of the patient's participation in the study or as required to meet local regulations (definitions and reporting requirements, see Section 7.4.1).
- Post study related safety reports, drug overdose, interaction, abuse, misuse, or medication error (see Section 7.6).

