## 9.4 Safety Analysis Plan

The analysis of safety will be based on the safety population.

All AEs (including events likely to be related to the underlying disease, or a concomitant illness or medication or clinically significant abnormalities in laboratory parameters or vital signs) will be displayed in summary tables and listings.

Incidence of AEs will be given as numbers and percentages of subjects with:

- Any AE
- Any SAE
- Any AE probably or possibly related to the IMP
- Any AE temporally related (within 24 hours after end of infusion) to the IMP
- Any severe AE
- Any withdrawal due to AE
- Any AE by Medical Dictionary for Regulatory Activities (MedDRA) preferred term (descending frequency)
- Any AE temporally related (within 24 hours after end of infusion) by MedDRA preferred term (descending frequency)
- Any AE by MedDRA system organ class (SOC)
- Any AE temporally related (within 24 hours after end of infusion) by MedDRA SOC

Summary tables for AEs will be given by SOC and preferred term. Additionally, AEs will be summarised by severity and relationship to the IMP

The MedDRA coded terms and the corresponding original (verbatim) terms used by the investigator will be listed.

For laboratory variables (analyses of haematology, clinical chemistry, and thrombogenicity), the mean, standard deviation, median, and range will be presented per time point. Laboratory variables will also be presented graphically. Intra-individual changes between pre-infusion and the respective post-infusion time points will be analysed using shift tables and graphical presentations. Fibrinogen inhibitor testing data will be summarized in frequency tables.

For vital signs, the mean, standard deviation, median, and range will be presented per time point (original values and intra-individual changes between pre-infusion and the respective post-infusion time points). Physical examination data will be presented in frequency tables.

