14.3.2	T	Summary of Adverse Events number of subjects with any AE, SAE, Severe AE or possibly or probably related AE, AEs that begin within 24 hours of end of infusion	SAF
14.3.3	T	Number of subjects with treatment-emergent adverse events by system organ class and preferred term – SAF	SAF
14.3.4	T	Number of subjects with treatment-emergent possibly/probably related to study drug by system organ class and preferred term – SAF	SAF
14.3.5	T	Number of subjects with treatment-emergent adverse events temporally related (within 24 hours after end of infusion) to study drug by system organ class and preferred term - SAF	SAF
14.3.6	T	Number of subjects with treatment-emergent adverse events by severity by system organ class and preferred term – SAF	SAF

14.3.7	T	Summary of adverse events by age group (2-<6 years, 6 -<12 years) - SAF	SAF
14.3.8	L	Listing of treatment-emergent serious adverse events	SAF
14.3.9	L	Listing of deaths	SAF
14.3.10	L	Listing of adverse events leading to discontinuation of study medication or death	SAF
14.3.11	T	Statistics on laboratory values for each time point relative to bleeding and surgery events (2 sub-tables: Hematology, Clinical chemistry)	SAF
14.3.12	L	Abnormal laboratory value listing (2 sub-listings: Hematology, Clinical chemistry)	SAF
	T	Statistics on vital signs for each time point relative to bleeding and surgery events	SAF
14.3.13	L	Abnormal vital signs listing	SAF
14.3.14	L	Abnormal physical examination findings	SAF

*Listings will generally be sorted by age group and subject number*

16.2		Subject Data Listings (section 16.2 of the CSR)	
16.2.1.1	L	Prematurely discontinued subjects (inc. time in study and number of EDs)	All (enrolled subjects)
16.2.1.2	L	Study Completion – All enrolled subjects	All
16.2.2	L	Protocol violations and data issues flagged by “minor” and “major”	All
16.2.3	L	Disposition of subjects with respect to analysis populations	All screened subjects
16.2.4.1	L	Subject demographics – All enrolled subjects	All enrolled subjects
16.2.4.2	L	Medical history	All
16.2.4.3.1	L	Prior and concomitant medication	All
16.2.4.3.2	L	Co-medication used in the treatment of bleeding episodes	BLEED, BLEED-PP
16.2.4.3.3	L	Concomitant medication during surgery	Surg, Surg-PP
16.2.5.1	L	Octafibrin doses during study including reason for treatment	All
16.2.5.2	L	Deviations from the planned schedule of PK assessments	All
16.2.5.3	L	FIX concentrations (IU/mL) per assay during PK profile and recovery determination	All

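### As worded, the temporally related AE tables leave out reactions that start during an infusion, and repeat infusions in a bleed have no pre-infusion vital signs for the planned change analysis

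*SAP*

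**What the plan says.** **AE window.** Protocol 9.4 and SAP section 12 both list, among the incidences to be tabulated, "Any AE temporally related (within 24 hours after end of infusion) to the IMP". The same parenthesis recurs in their bullets by preferred term and by system organ class. SAP Table 14.3.5 covers events "temporally related (within 24 hours after end of infusion) to study drug by system organ class and preferred term". Table 14.3.2 instead counts "AEs that begin within 24 hours of end of infusion". Collection begins earlier: Protocol 7.4 records "All AEs occurring between the start of the first *Octafibrin* infusion and the end of the PK phase", with matching end points for bleeds and surgery.

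**Vital signs.** Protocol 9.4 plans to present "original values and intra-individual changes between pre-infusion and the respective post-infusion time points", and SAP section 12 repeats this. Neither names the baseline for a second or later infusion. In Protocol 6.1.3.2 the pre-infusion list for additional infusions in a bleed holds a TEE questionnaire and an item beginning "Blood draw for (within 30 minutes before infusion", under which come fibrinogen and thrombogenicity samples. The list before the last infusion (6.1.3.3) has the same structure without thrombogenicity. Vital signs are in neither list, nor in the daily assessments of 6.1.3.2. They do appear 1 hour after each of these infusions.

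**The concern.** The safety objective in Protocol 2.2 is to assess safety "including immunogenicity, thromboembolic complications, and early signs of allergic or hypersensitivity reactions". Immediate reactions can begin while the product is still running in. A reaction that makes staff stop the infusion has, by definition, begun before that infusion ended. A rule that starts counting at the end of the infusion leaves these cases out of the one set of AE tables based on timing rather than on the investigator's causality judgement.

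The vital-sign gap bears on the same objective, because Protocol 1.5 names hypotension among the symptoms of hypersensitivity. For a repeat infusion in a bleed, the only pre-infusion value in that episode is the Day 1 one, taken when the child presented with acute bleeding. A change measured from it mixes any effect of the later infusion with whatever happened in between.

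**Working it through.** The plan states no figure to reproduce. The check compares wordings, sizes the uncovered period and then compares schedules.

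**1. Wordings of the window**

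| Place | Reference point | Is onset during the infusion included? |
|---|---|---|
| Protocol 9.4 | after the end | no, read literally |
| SAP section 12 | after the end | no, read literally |
| SAP Table 14.3.5 | after the end | no, read literally |
| SAP Table 14.3.2 | within 24 hours of the end | not settled |
| Protocol 7.4 (collection) | from the start of the first infusion | yes |

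Neither document adds onset during the infusion to the temporally related definition. The one route back in is an earlier infusion: if a repeat infusion runs within 24 hours of the end of the previous one, that earlier window covers it.

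**2. Length of the uncovered period**

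Inputs:
- Concentration 20 mg/mL (Protocol Table 1).
- Administration as "intravenous (i.v.) bolus injection not exceeding an injection rate of 5 mL per minute" (5.5.2).
- PK dose 70 mg/kg (5.4.1).
- Treatment dose = (target − measured level) / 1.77 (5.4.2), with 1.77 in mg/dL per mg/kg as in the formula's denominator and SAP section 3.
- Targets 100 and 150 mg/dL, lower limits 80 and 130 mg/dL (5.4.3).
- Body weights of 5 to 40 kg are my assumption; the documents give none.

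Minimum duration (min) = dose (mg/kg) × weight (kg) / 20 / 5.

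| Infusion | Dose, mg/kg | 5 kg | 10 kg | 20 kg | 40 kg |
|---|---|---|---|---|---|
| PK | 70 | 3.5 | 7.0 | 14.0 | 28.0 |
| First, target 100, baseline 0 | 100/1.77 = 56.5 | 2.8 | 5.6 | 11.3 | 22.6 |
| First, target 150, baseline 0 | 150/1.77 = 84.7 | 4.2 | 8.5 | 16.9 | 33.9 |
| Repeat, rise of 20 mg/dL | 20/1.77 = 11.3 | 0.6 | 1.1 | 2.3 | 4.5 |

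The 20 mg/dL in the last row is the gap between target and lower limit (100 − 80 and 150 − 130), so it represents a small top-up. These are lower bounds on duration, since a slower rate lengthens them. A measurable baseline would shorten the two first-treatment rows.

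**3. Vital-sign schedule, infusion by infusion**

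| Infusion | Before | After |
|---|---|---|
| PK | yes | 1 h and 3 h |
| First of a bleed (6.1.3.1) | yes | 1 h and 3 h |
| Additional, in a bleed (6.1.3.2) | none, in daily or pre-infusion list | 1 h |
| Last, in a bleed (6.1.3.3) | none | 1 h, and at the final assessment |
| Post-operative (6.1.4.2) | in the daily list, not timed to the infusion; none in the pre-infusion list | 1 h |

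The bleeding flow chart agrees with the text as far as its layout can be read. For surgery, the text of 6.1.4.2 puts vital signs on every post-operative day, whereas footnote [i] of the surgical flow chart limits the daily column to days without an infusion. On infusion days the two cannot both hold.

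**The case against.** The strongest reply on the window is that the 24 hours can be read as an upper cut-off only, and that Table 14.3.2 does not say after. A sensible programmer might include onset during the infusion. That is fair, and it means the exclusion is not settled in every place. It does not remove the problem: one event could count in Table 14.3.2 and not in Table 14.3.5, with the choice made at programming.

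A reader might infer that such reactions would go unreported. The documents do not support that. Events are collected from the start of the first infusion. They enter the any-AE count, the serious, severe and related counts where they qualify, and the per-subject listing with onset, causality and treatment at the time. Nor does either document designate the temporally related tables as the hypersensitivity display.

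On vital signs, a reader might infer that no change can be computed, or that Day 1 pre-infusion is the only earlier value. Neither holds. A change from Day 1 is computable and fits the SAP's table of vital signs by time point relative to each bleed or surgery. Values also exist 1 and 3 hours after the Day 1 infusion and 1 hour after each additional one. None of these is a scheduled pre-infusion value for the repeat infusion itself. Clinically significant vital-sign abnormalities are also captured as AEs, and abnormal values are listed (14.3.13). Finally, it would be wrong to say that post-operative infusions have no earlier vital signs that day; the text schedules them, and the fault there is the conflict with the flow chart.

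**Conclusion.** Two limited points hold.

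First, on its literal wording the temporally related definition omits AEs that start during an infusion, unless an earlier infusion's window covers them. At the maximum rate and assumed weights of 5 to 40 kg, the omitted period is at least about 3 to 34 minutes for the PK infusion and for first treatment infusions from a zero baseline, and about 1 to 5 minutes for a 20 mg/dL top-up. The number of events affected cannot be derived from the documents. With the planned minimum of 12 children, moving one child in or out of the count shifts that incidence by 1/12, about 8 percentage points. The effect is confined to the temporally related rows and tables.

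Second, no infusion after the first in a bleed has a scheduled pre-infusion vital-sign value of its own, so for those infusions the planned change lacks a same-infusion baseline and the SAP does not name a substitute. The paired analysis remains sound for the PK infusion and the first infusion of each bleed. For surgery the finding is only that text and flow chart contradict each other.

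The study is descriptive, so no test or primary conclusion is affected. The points merit correction because they touch a named safety objective and are inexpensive to fix.

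**What to change.** 1. In Protocol 9.4, SAP section 12 and Tables 14.3.2 and 14.3.5, define temporally related as onset from the start of an infusion to 24 hours after its end. The cost is one phrase in each place; the temporally related count may rise.
2. For vital signs in bleeds, choose one of two routes. Either state in SAP section 12 that paired changes are limited to infusions with their own pre-infusion value, and label any change from the Day 1 pre-infusion value as such; this costs a sentence and table footnotes. Or add vital signs to the pre-infusion lists in Protocol 6.1.3.2 and 6.1.3.3, the matching synopsis lists and the bleeding flow chart, and compute each change within its own infusion; this costs a few minutes of measurement before each repeat infusion and a protocol amendment.
3. Reconcile the daily post-operative list (synopsis and Protocol 6.1.4.2) with footnote [i] of the surgical flow chart, so that it is clear whether vital signs are taken on days with an infusion and, if they are to serve as a baseline, when relative to it.

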#### 14 TABLES, FIGURES AND LISTINGS (SECTION 14 AND 16.2 OF THE CSR)

The following tables, figures and lists will be generated.

All output will be headed with an appropriate heading specifying study ID and title.

All output will be dated and have page numbers in the form 'Page x of y'.

The order and numbering of the various parts of the Clinical Study Report may not necessarily follow the scheme used below.

All statistical output will identify the underlying analysis populations (see section 6), and indicate the number of subjects/ events in this population (N) and the number of subjects/events actually contributing to the particular output (n).

Due to the small number of patients some of the tables described below may be not generated in the final analysis and replaced by a listing comprising the same variables as in the respective table. If no patient is excluded from the PP population all tables, figures and listings will be done only for the ITT population.

Analysis populations			
14.1.1.1	T	Subject Disposition and analysis populations Number of subjects enrolled, erroneously enrolled, treated, completed, withdrawn	All
14.1.1.2	T	Bleeding episodes Analysis Populations	BLEED
14.1.1.3	T	Surgery Analysis Populations	SURG
14.1.2	L	Protocol Deviations Listing of all major and minor protocol violations together with the reason of violation and exclusion from analysis populations	SAF
14.1.3	L	Compliance to Schedule of PK assessments PK assessments not performed according to the schedule	ITT, PK-PP

Demographic Data			
14.1.4	T	Number of subjects per center, age-group and analysis population	SAF
14.1.5	T	Statistics on age, body height, body weight, body mass index, ethnicity and blood type	ITT, PP
14.1.6	T	Statistics on duration of treatment	ITT, PP
14.1.7	L	Underlying gene defects for FIX and family history of fibrinogen deficiency	ITT, PP
14.1.8	T	FIX activity (%) at screening	ITT, PP
14.1.9	T	Frequency of use of prior and concomitant medications by ATC class (without surgeries) (2 sub-tables: 1 for prior, 1 for concomitant)	ITT, SAF
14.1.10	T	Use of Factor IX concentrates within ½ year before start of study treatment	ITT, SAF

	Bleeding episodes
--	-------------------

14.2.1	T	Subjects included in bleeding analysis (first, minor, major, total) and number of bleedings (minor, major, total)	ITT, PP
14.2.2	T	Number and frequency of bleeding episodes per subject	BLEED, BLEED-PP
14.2.3	T	Frequency of bleeding episodes per age group and in total	BLEED, BLEED-PP (age groups)
14.2.4	T	First bleeding episode per type of BE (spontaneous, traumatic, post-operative, other)	BLEED, BLEED-PP
14.2.5	T	Bleeding episodes per type of BE (spontaneous, traumatic, post-operative, other)	BLEED, BLEED-PP
14.2.6	T	Site of first bleeding episode	BLEED, BLEED-PP
14.2.7	T	Site of bleeding episodes	BLEED, BLEED-PP
14.2.8	T	Treatment duration of the first bleeding episode	BLEED, BLEED-PP
14.2.9	T	Treatment duration of bleeding episodes	BLEED, BLEED-PP
14.2.10	T	Severity of first bleeding episode (mild, moderate, severe)	BLEED, BLEED-PP
14.2.11	T	Severity of bleeding episodes (mild, moderate, severe)	BLEED, BLEED-PP
14.2.12	T	Efficacy assessment (final outcome) of treatment of first bleeding episode a) Four point scale (14.2.11.1) (excellent, good, moderate, none) b) Two point scale (successfully treated (excellent or good), not successfully treated (moderate or none) (14.2.11.2))	BLEED, BLEED-PP (age groups)
14.2.13	T	Statistics on successfully treated first bleeding episodes (two-sided 95% Clopper-Pearson confidence interval)	BLEED, BLEED-PP
14.2.14	T	Efficacy assessment (final outcome) of treatment of bleeding episodes a) Four point scale (14.2.13.1) (excellent, good, moderate, none) b) Two point scale (successfully treated (excellent or good), not successfully treated (moderate or none) (14.2.13.2))	BLEED, BLEED-PP (age groups)
14.2.15	L	Treatment details for each bleeding episode per patient (incl. exposure days, number of injections, dosing inc. batch numbers, consumption of Octafibrin, haemostatic co-medication)	BLEED, BLEED-PP
14.2.16	T	Statistics on successfully treated bleeding episodes (two-sided 95% Clopper-Pearson confidence interval)	BLEED, BLEED-PP
14.2.17	T	Statistics on MCF and fibrinogen activity for samples taken before and 1 hour after the end of the first infusion (including confidence interval for the difference)	BLEED, BLEED-PP
14.2.18	T	Statistics on MCF and fibrinogen activity for samples taken before and 1 hour after the end of the first infusion separated by four/two point efficacy scale	BLEED, BLEED-PP
14.2.19	F	Boxplot MCF and fibrinogen activity for samples taken before and 1 hour after the end of the first infusion separated by four/two point efficacy scale	BLEED, BLEED-PP
14.2.20	T	Statistics on final efficacy assessment of the IDMEAC and the efficacy assessment of the investigator	BLEED, BLEED-PP

		Surgeries	
14.2.21	T	Subjects included in surgery analysis (minor, major, total) and number of surgical procedures (minor, major, total)	ITT, PP
14.2.22	L	Surgery Characteristics (type and site, pre-planned, severity, expected and actual duration, expected and actual blood loss, age group)	Surg, Surg-PP
14.2.23	L	Fibrinogen levels pre-, intra- and post-operative, as well as pre- and post-infusion for each injection will be listed	Surg, Surg-PP

14.2.23	L	Efficacy Evaluation of the Use of Octafibrin in Surgical Procedures a) at end of surgery (by the surgeon) b) post-operatively (by the haematologist) c) overall (by the IDMEAC) using the four point scale (excellent, good, moderate, none) as described in chapter 3.3.6 of the SAP	Surg, Surg-PP
---------	---	--	---------------

Pharmacokinetics			
14.2.24	T	Doses administered for PK and recovery assessments – PK-PP population summary statistics for total dose and dose per kg b.w. for PK assessments (inc. nominal dose and actual dose calculated from potency of the batch)	PK, PK-PP
14.2.25	F	Mean (+/- SD) fibrinogen levels (IU/mL) – PK-PP for each of the PK assessments Summarized Plot of PK profiles mean (+/- SD) plots	PK, PK-PP
14.2.26	T	Statistics on FIX concentrations (%), nominal time points - by age group and combined	PK, PK-PP (age groups)
14.2.27	T	Statistics on AUC last , AUC, AUC norm , and AUMC of FIX, calculations based on actual time points - by age group and combined	PK, PK-PP (age groups)
14.2.28	T	Statistics on C max , C max,norm and recovery of FIX (%) after injection of Octafibrin based on the actual potency, per performed recovery - by age group and combined	PK, PK-PP (age groups)
14.2.29	T	Statistics on T max (h) after injection of Octafibrin per performed recovery - by age group and combined	PP, PK-PP (age groups)
14.2.30	T	Statistics on T 1/2 and MRT after injection of Octafibrin based on the actual potency, - by age group and combined	PK, PK-PP (age groups)
14.2.31	T	Statistics on CL and V ss after injection of Octafibrin based on the actual potency, - by age group and combined	PK, PK-PP (age groups)

Safety			
14.3.1	T	Extent of exposure SAF number of infusions, total dose (IU and IU/kg b.w.) per reason for administration and in total	SAF
14.3.2	T	Summary of Adverse Events number of subjects with any AE, SAE, Severe AE or possibly or probably related AE, AEs that begin within 24 hours of end of infusion	SAF
14.3.3	T	Number of subjects with treatment-emergent adverse events by system organ class and preferred term – SAF	SAF
14.3.4	T	Number of subjects with treatment-emergent possibly/probably related to study drug by system organ class and preferred term – SAF	SAF
14.3.5	T	Number of subjects with treatment-emergent adverse events temporally related (within 24 hours after end of infusion) to study drug by system organ class and preferred term - SAF	SAF
14.3.6	T	Number of subjects with treatment-emergent adverse events by severity by system organ class and preferred term – SAF	SAF

14.3.7	T	Summary of adverse events by age group (2-<6 years, 6 -<12 years) - SAF	SAF
14.3.8	L	Listing of treatment-emergent serious adverse events	SAF
14.3.9	L	Listing of deaths	SAF
14.3.10	L	Listing of adverse events leading to discontinuation of study medication or death	SAF
14.3.11	T	Statistics on laboratory values for each time point relative to bleeding and surgery events (2 sub-tables: Hematology, Clinical chemistry)	SAF
14.3.12	L	Abnormal laboratory value listing (2 sub-listings: Hematology, Clinical chemistry)	SAF
	T	Statistics on vital signs for each time point relative to bleeding and surgery events	SAF
14.3.13	L	Abnormal vital signs listing	SAF
14.3.14	L	Abnormal physical examination findings	SAF

*Listings will generally be sorted by age group and subject number*

16.2		Subject Data Listings (section 16.2 of the CSR)	
16.2.1.1	L	Prematurely discontinued subjects (inc. time in study and number of EDs)	All (enrolled subjects)
16.2.1.2	L	Study Completion – All enrolled subjects	All
16.2.2	L	Protocol violations and data issues flagged by “minor” and “major”	All
16.2.3	L	Disposition of subjects with respect to analysis populations	All screened subjects
16.2.4.1	L	Subject demographics – All enrolled subjects	All enrolled subjects
16.2.4.2	L	Medical history	All
16.2.4.3.1	L	Prior and concomitant medication	All
16.2.4.3.2	L	Co-medication used in the treatment of bleeding episodes	BLEED, BLEED-PP
16.2.4.3.3	L	Concomitant medication during surgery	Surg, Surg-PP
16.2.5.1	L	Octafibrin doses during study including reason for treatment	All
16.2.5.2	L	Deviations from the planned schedule of PK assessments	All
16.2.5.3	L	FIX concentrations (IU/mL) per assay during PK profile and recovery determination	All
16.2.5.4	L	PK parameters Octafibrin	All
16.2.5.5	L	Dose of Octafibrin for surgical reasons	Surg, Surg-PP
16.2.5.6	L	Pre-, intra-, and post-operative FIX plasma levels	Surg, Surg-PP
16.2.6.1	L	Bleeding episodes during study incl. efficacy assessment of treatment	BLEED, BLEED-PP
16.2.6.2	L	Bleeding episodes, doses and changes in dose per infusion for each bleeding episode during study	BLEED, BLEED-PP
16.2.6.3.1	L	Surgeries: Description and outcome of surgical procedures	Surg, Surg-PP
16.2.6.3.2	L	Surgeries: Description and assignment to SURG/SURG-PP populations including reasons for exclusion	Surg, Surg-PP
16.2.6.3.3	L	Surgeries: Blood loss (planned and actual), duration of surgery (planned and actual)	Surg, Surg-PP
16.2.7.1	L	Treatment emergent adverse Events (inc. indicator for phase of study: PK, surgery, bleeding)	All

16.2.7.2	L	Possibly/probably related adverse events	All
16.2.7.3	L	Non-treatment emergent adverse events	All
16.2.8.1	L	Laboratory assessments (Haematology, Clinical chemistry) (2 sub-listings: hematology, clinical chemistry )	All
16.2.8.2	L	FIX, inhibitor and FIX antibodies determinations at baseline and during study	All
16.2.8.3	L	Vital signs	SAF
16.2.8.4.1	L	Physical examination	All
16.2.8.4.2	L	Abnormal findings of physical examination	SAF
16.2.9	L	Additional comments provided in the CRF	All
		Detailed PK analysis	
16.2.10	F, PK	Graphs and WinNonlin outputs for individual PK Analysis	

16.4		Individual Subject Data Listings (section 16.4 of the CSR)
		Note: SAS datasets including individual subject data will be prepared. Datasets will be available on request, e.g. for an electronic submission according to CDISC /SDTM. Therefore no listings will be prepared for Section 16.4.

